8.2 Secondary outcomes

8.2.1 Clinical

UTI recurrence

- Relapse (recurrent infection with the original bacterial strain) up to final follow-up, 30 days post-randomisation.
- Reinfection (recurrent infection with a different bacterial strain) up to final follow-up, 30 days post-randomisation.

Individual components of the primary outcome

- Fever resolution at the primary outcome assessment visit.
- No additional systemic antibiotic prescription by the primary outcome assessment visit

Microbiological cure

• Urine sterilisation at the primary outcome assessment visit.

Antibiotic-associated adverse events

• Antibiotic-associated adverse events, including diarrhoea, rash, and candida infections.

Adherence to trial drug

• No more than one missed dose from the allocated full course, as logged on the medicine tracker page of the CURLY app and no additional dose(s) beyond the assigned treatment duration.

Antimicrobial resistance & ESBL rates

- Overall rates of antibiotic resistance of urinary pathogens within pre- and post-treatment urine samples.
- Regional rates of antibiotic resistance.
- Identification of ESBL-producing organisms within post-treatment urine samples.

Quality of life – CHU9D

• Differences in quality of life (using the Child Health Utility instrument CHU9D) between the different treatment duration arms (40).

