2.2 Main trial objectives

2.2.1 Clinical objectives

- 1. To determine the optimal (shortest effective) cefalexin duration for the treatment of febrile UTIs in children, to achieve clinical cure (**primary objective**).
- 2. To assess the impact of cefalexin treatment duration on UTI recurrence (relapse or reinfection) up to 30 days post-randomisation.
- 3. To assess the impact of cefalexin treatment duration on microbiological cure and antimicrobial resistance.
- 4. To assess the impact of cefalexin treatment duration on antibiotic-associated adverse events, including diarrhoea, rashes, and candida infections.
- 5. To assess patient adherence to the trial drug across the treatment duration arms.
- 6. Differences in quality of life (using the Child Health Utility instrument CHU9D) between the different treatment duration arms.

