7.1.3 Duration of cefalexin

Trial participants will be randomised to either 3 days (6 doses), 5 days (10 doses), 6 days (12 doses), 8 days (16 doses) or 10 days (20 doses) of cefalexin.

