7.4 Premature discontinuation of cefalexin

Cefalexin may be discontinued prior to a participant completing the assigned treatment course duration. Reasons for this include:

- The baseline urine culture result demonstrates a UTI caused by a cefalexin-resistant pathogen. As per standard practice, cefalexin will be discontinued and a different antibiotic with proven pathogen susceptibility will be commenced.
- The baseline urine culture result demonstrates no growth or below threshold growth. Sites will be permitted to inform families and advise discontinuation of cefalexin therapy, should this be their standard practice.
- A significant adverse reaction to cefalexin.
- Failure to tolerate oral cefalexin treatment and/or other clinical deterioration.

All such decisions are at the discretion of the treating clinician. The reason for any premature discontinuation of cefalexin will be logged on the Change of Status and Primary Outcome Assessment eCRF by the local study team.

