7.7 Adherence

In contrast to trials which investigate medications in tablet form, it will not be possible to dispense a rationed volume of liquid medication appropriate for the allocated duration arm. In paediatric practice, medication suspensions are reconstituted according to the manufacturer's instructions, and any excess volume in the bottle allows for common issues of spillage or doses being spat out by the child. The dispensing of these standard volume bottles creates a potential for non-adherence with allocated cefalexin duration, and it will therefore be necessary to monitor adherence, which will

be defined as no more than one missed dose from the allocated full course, as logged on the medicine tracker page of the CURLY app, and no additional dose(s) beyond the assigned treatment duration. The app will support adherence by providing a visual prompt to parents/guardians about the duration of the allocated cefalexin, and when their child's final antibiotic dose is due.

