14.1 Sample size

We aim to randomise 705 children in a 1:1:1:1:1 ratio to receive either 3, 5, 6, 8 or 10 days of cefalexin. We estimate that this will provide us with 500 patients (100 in each duration) for our microbiological population. The "DURATIONS design" estimates that a sample size of 500 patients divided into a moderate number of broadly equidistant arms (5–7 arms) is required to estimate the duration—response curve satisfactorily (29). Simulations based on plausible scenarios showed that such a sample size was enough to estimate the curve within 5% average absolute error in 95% of simulations. Power for the optimal duration analysis is dependent on the assumed shape of the response curve. We will task the DMC with assessing a more accurate simulation of the analysis at the end of the internal pilot period (using concurrent data) to ascertain if our sample size assumptions remain robust, or whether we require a larger sample size.

Analysis in both the microbiological-confirmed population (those with proven UTI who are not resistant to cefalexin) and the intention-to-treat (ITT) population will be carried out. Given that randomisation occurs before urine culture results are known, the number of patients not included in the microbiological-confirmed population should be equally distributed between treatment arms, thus limiting risk of bias.

Of the population it is estimated that:

- ~12% of participants will not have a proven UTI on urine culture, despite initial clinical symptoms and/or positive point-of-care test (information estimated from a local audit of 530 urine culture results at Birmingham Children's Hospital, 95% CI 9.3% 14.9%).
- ~10% of proven UTIs (8.8% of entire population) involve a cefalexin-resistant pathogen (10).
- ~10% will be lost to follow up.

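### The adherence outcome allows one missed dose whether the course is 6 or 20 doses, and counts stops that section 7.4 provides for as missed doses, so it does not compare families' adherence fairly across arms

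*Protocol*

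**What the plan says.** The fifth clinical objective in section 2.2.1 is a comparison between arms: "To assess patient adherence to the trial drug across the treatment duration arms".

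The outcome in section 8.2.1 has two parts. The first is "No more than one missed dose from the allocated full course, as logged on the medicine tracker page of the CURLY app". The second is "no additional dose(s) beyond the assigned treatment duration". Section 7.7 repeats the first part ("be defined as no more than one missed dose from the allocated full course"), and the Trial Summary gives the same rule in short form. None of the three scales the allowance to course length or exempts a stop directed by the site.

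Section 7.1.3 fixes the courses as "either 3 days (6 doses), 5 days (10 doses), 6 days (12 doses), 8 days (16 doses) or 10 days (20 doses").

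Section 7.4 states that cefalexin is stopped and replaced when the baseline culture shows a resistant pathogen. For no growth or below-threshold growth it says: "Sites will be permitted to inform families and advise discontinuation of cefalexin therapy, should this be their standard practice". Section 14.1 expects that about "12% of participants will not have a proven UTI on urine culture", and that 8.8% of all participants will have a cefalexin-resistant pathogen. Table 9 in section 11.2 puts the microbiology report at typically 48 hours after urine collection.

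**The concern.** The definition has two features that do not reflect how families behave.

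First, the allowance is an absolute count. A family in the 10-day arm has 20 chances to miss or forget to log a dose and is forgiven one. A family in the 3-day arm has 6 chances and is forgiven one. Identical behaviour per dose gives different adherence rates.

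Second, missed doses are counted against the whole allocated course. A child whose treatment is stopped on the site's advice has many untaken doses and fails the rule, although the family did what it was told.

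The objective is a comparison across durations. A difference that the rule itself produces could be read as families coping better with short courses. The open-label design and the intended use of the results in guidelines (section 23.2) make that reading easy to pick up.

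**Working it through.** **Inputs from the protocol.** Doses per arm n = 6, 10, 12, 16, 20 (7.1.3). Allowance: 1 missed dose (7.7, 8.2.1). Resistant pathogen: 8.8% of all participants; no proven UTI: about 12% (14.1). Culture report: typically 48 h (11.2).

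**Inputs not in the protocol.** The chance q of missing or not logging a dose is assumed, with range 1% to 10%, equal in all arms. Doses are first taken as independent, then as clustered within families.

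**The plan's own figures.** The protocol gives no adherence rate or target. The culture shares do feed its sample size, which reproduces: 0.88 × 0.10 = 8.8%; 500 / (0.88 × 0.90 × 0.90) = 701.5, against the stated 705.

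**Step 1: tolerance as a share of the course.** 1/n = 16.7%, 10.0%, 8.3%, 6.3%, 5.0% for 3, 5, 6, 8, 10 days.

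**Step 2: chance of meeting the missed-dose rule.** P(at most 1 missed) = (1−q)^n + n·q·(1−q)^(n−1).

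Example at q = 5%: for 6 doses, 0.735 + 0.232 = 0.967; for 20 doses, 0.358 + 0.377 = 0.736 (from unrounded terms).

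| q | 3 d | 5 d | 6 d | 8 d | 10 d |
|---|---|---|---|---|---|
| 1% | 99.9% | 99.6% | 99.4% | 98.9% | 98.3% |
| 2% | 99.4% | 98.4% | 97.7% | 96.0% | 94.0% |
| 5% | 96.7% | 91.4% | 88.2% | 81.1% | 73.6% |
| 10% | 88.6% | 73.6% | 65.9% | 51.5% | 39.2% |

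The rate falls with duration at every q tried.

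**Step 3: clustering within families.** With a beta-binomial model and an assumed intra-family correlation of 0.3, 3 v 10 days is 98.5% v 96.5% at q = 1%, 97.0% v 93.0% at 2% and 92.5% v 83.0% at 5%. The gap at 5% drops from 23.1 to 9.5 points and at 2% from 5.4 to 4.0. At 1% it stays at about 2 points. The direction does not change.

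**Step 4: stops on a culture result.** With doses every 12 hours from hour 0, the untaken doses are:

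| Stop acted on at | Doses taken | 3 d | 5 d | 6 d | 8 d | 10 d |
|---|---|---|---|---|---|---|
| 48 h | 4 | 2 | 6 | 8 | 12 | 16 |
| 60 h | 5 | 1 | 5 | 7 | 11 | 15 |
| 72 h | 6 | 0 | 4 | 6 | 10 | 14 |

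More than one untaken dose means non-adherent. At 48 h every arm fails. From about 60 h, once the fifth dose has been taken, the stop itself no longer makes a 3-day child fail, while the other four arms all still do.

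**Step 5: how many children.** Resistant: 0.088 × 705 = 62. No proven UTI: 0.12 × 705 = 85 at most. Only part of the 85 can be stopped for this reason: section 7.4 leaves it to site practice and names only no growth and below-threshold growth. Section 14.3 treats mixed growth as a separate group, and it may lie within the 12%.

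**Step 6: the alternative measure.** The expected proportion of instructed doses taken is 1 − q in every arm, so equal behaviour gives equal results.

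**The case against.** *The rule measures delivery of the allocated duration.* Sections 5.1.3 and 7.7 give that as the reason for monitoring doses. For that purpose completion of the allocated course is legitimate, and stops should count. This stands as a reason to keep the yes/no figure. It does not make that figure a fair comparison of patients' adherence, which is what the objective asks for.

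*The second clause may pull the other way.* A reader might infer that the whole outcome must fall with duration. The protocol does not support that. Section 7.7 gives surplus suspension as the source of non-adherence, and short courses leave more of it: at 10–11.99 kg a 3-day course uses 18 ml of a 100 ml bottle and a 10-day course 60 ml (Table 2). To cancel the missed-dose gap, over-running would have to remove about 5% (1 − 0.940/0.994, q = 2%) to 24% (1 − 0.736/0.967, q = 5%) more of the 3-day arm than of the 10-day arm. That is possible. The result would then be two opposing effects merged in one figure.

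*Culture-directed stops do not create a gradient.* A reader might be tempted to add 8.8% and 12% and charge the full 20.8% to the longer arms only. That needs every stop to come after the fifth dose, every site to advise stopping, and all of the 12% to be stoppable. None of these is stated. The 48 h also runs from urine collection, which section 9.1.1 places before consent, so fewer doses may have been taken by then. When the 3-day arm is spared, the other four are affected alike.

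*The analysis set may remove these children.* The protocol does not name the set for this outcome. In the microbiological-confirmed population (14.2), resistant and unproven cases are absent and the second problem disappears. The fixed allowance remains.

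*The consequence is uncertain.* Section 14.5 plans no model or test for adherence. This limits the weight of the point.

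**Conclusion.** The point holds for the missed-dose component. A fixed allowance of one dose across courses of 6 to 20 doses makes that component fall with duration under identical behaviour or identical logging. The gap between 3 and 10 days is about 2 points at a 1% miss rate, 5 at 2% and 23 at 5% if doses are independent. At an assumed intra-family correlation of 0.3 it is about 2, 4 and 10 points. The direction does not depend on these assumptions as tested; the size does. The net direction of the full outcome is not determined, because of the extra-dose clause.

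Separately, the wording labels children stopped on a culture result as non-adherent: 8.8% of participants, plus an unknown part of the 12% without proven UTI, if all randomised children are tabulated. The protocol does not say so expressly; it follows from counting against the full allocated course. This affects all arms at 48 h and spares only the 3-day arm from about 60 h.

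This is a definition fixed in the protocol, not a detail left to the SAP. It concerns one secondary outcome and leaves the primary analysis untouched.

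**What to change.** In sections 7.7 and 8.2.1:

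- For the adherence objective, report by arm the proportion of instructed doses taken, counting doses only up to the date of any site-directed stop.
- Show site-directed stops by arm and reason as a separate line.
- Show doses beyond the assigned duration by arm as a separate line, so that over-running stays visible.
- Keep the existing yes/no definition, described as completion of the allocated course, with a note that its allowance is not scaled to course length.

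The cost is a wording change and a derivation from data already planned: app dose logs and the reason for stopping recorded under section 7.4. Section 7.4 names the reason but not the date, so the date must come from the Change of Status eCRF or, failing that, from the last logged dose. Using the last logged dose would hide any doses missed just before the stop. The report carries two or three descriptive lines in place of one figure. No treatment rule changes.

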8.2.2 Economic

Health economics

• An incremental cost-utility analysis will determine the Cost per Quality Adjusted Life Years of the different treatment durations over the follow-up period.

9. TRIAL PROCEDURES

9.1 Schedule of assessments

The frequency of follow-up visits and assessments are detailed in the **Schedule of Assessments** (Table 4).

Trial visits and contact schedules should be determined and assigned for each child at randomisation, and children should be followed on that schedule, until the final follow-up visit, even if their trial medication is discontinued prematurely. The schedule defines visit dates (with windows) necessary for data collection.

The face-to-face ED follow-up for the primary outcome assessment will be scheduled in advance, ideally at 16 days post-randomisation, but with a window of ±2 days to allow for weekends and public holidays. If the visit is missed without notice, the research team will endeavour to contact the parent/guardian by phone. If the primary outcome follow up can only be conducted by phone, the parent/guardian will be encouraged to provide a sample of their child's urine remotely.

During any unscheduled acute events, the child can be seen face-to-face if attending the randomising centre. Otherwise, a telephone contact can be arranged.

Table 4: Schedule of Assessments

Day of Trial	dO	d0	d0-d10	48-72 hrs post- cefalexin completion	d16 (±2d)	d30 (±2d)	Any
Visit	Screening	Baseline	Monitoring via CURLY app	Fit & well check	Primary outcome assessment	Recurrence follow-up	Any acute event
At site/remote	Site	Site	Remote	Remote	Site	Remote	Either
Point-of-care dipstick urinalysis	х				x		(X)
Urine sample sent for culture, microscopy & antibiotic sensitivity	х				x	х	(X)
Eligibility check	х						
Valid informed consent/assent		х					
Relevant medical history taken		х					
Documentation of relevant physical examination findings		х			(X)	(X)	(X)
Symptom checklist		Х	х	х	х	х	(X)
CHU9D questionnaire		Х			х	х	
Randomisation		Х					
Allocation of trial number		х					
Cefalexin prescription & dispensing		х					
Setup of CURLY app		Х					
Education/advice to parent/guardian		х					
Concomitant medications			х		х	х	
Log of administration of cefalexin doses			x				
Adverse event reporting			х	х	х	х	х
Reminder text/email on final day of cefalexin			x				
Health resource use questionnaire				х	х	х	х
Stool sample or rectal swab					(X)*		

 $(X)^* = Optional sample collection participants only (after optional consent)$

9.1.1 Routine ED care prior to consent

- History and physical examination as part of routine ED assessment.
- Patient weight.
- Urine sample: point-of-care dipstick urinalysis.
- Urine sample: sent to lab for routine microscopy, culture, and antibiotic sensitivity.

9.1.2 Trial procedures at baseline ED visit

- Confirmation of inclusion and exclusion criteria.
- Informed consent/assent.
- The following baseline information will be obtained:
 - Demographic information including sex, ethnicity, and home postcode (for subsequent determination of indices of deprivation), to ensure results are generalisable.
 - \circ $\;$ Medical history and documentation of relevant medical diseases.
 - Documentation of usual urinary continence status of child.
 - Documentation of relevant physical examination findings from this ED attendance, including weight, temperature, and heart rate.
 - Standardised symptom checklist including those commonly associated with UTIs.
- Quality of life assessment (using CHU9D questionnaire).
- Randomisation and allocation of trial number.
- Cefalexin prescription and dispensing.
- Set-up of CURLY trial app and documentation of parent/guardian preferred contact details (email address and/or mobile phone number).
- Education and advice to parent/guardian (± child): routine clinical discharge safety netting advice.
- Education and advice to parent/guardian (± child): trial-specific instructions.

9.1.3 Remote data collection during cefalexin course (using CURLY trial app)

- Log of administration of cefalexin doses.
- Log of administration of relevant concomitant medicines (paracetamol, ibuprofen, and any non-trial antibiotic).
- Standardised symptom checklist including those commonly associated with UTIs, and those associated with side effects of cefalexin.
- Text/email alert will be sent to the parent/guardian on the final day of treatment, reminding them that the cefalexin is due to finish that day, but recommending medical review if their child's symptoms are not resolving.

9.1.4 Remote data collection 48 – 72 hours after end of treatment (via text/online questionnaire)

- Standardised symptom checklist including those commonly associated with UTIs, and those associated with side effects of cefalexin for "fit and well" check.
- Any acute illnesses requiring assessment by a healthcare provider since baseline ED visit, including whether any antibiotics were issued.
- Adherence review by site research team monitoring the app data.
- Health Resource Usage questionnaire.

9.1.5 Face-to-face ED primary outcome assessment at 16 days post-randomisation

- Standardised symptom checklist including those commonly associated with UTIs, and those associated with side effects of cefalexin.
- Any acute illnesses requiring assessment by a healthcare provider since last protocol contact, including whether any antibiotics were issued.
- Antibiotic treatment since last protocol contact, including, as appropriate, adherence to CURLY treatment and whether any additional/new antibiotic prescriptions were issued.
- Quality of life assessment (using CHU9D questionnaire).
- Urine sample for (i) point-of-care urinalysis and (ii) urine microscopy, culture and antibiotic sensitivity.
- Health Resource Usage questionnaire.

Should the child have any signs or symptoms of a UTI, the following will also be recorded:

 Relevant physical examination findings including vital parameters (temperature and heart rate).

The following will be obtained from children enrolled at sites participating in optional sample collection (and where additional consent/assent is given):

Stool sample or rectal swab (see Section 24.1)

9.1.6 Remote follow-up for recurrence at 30 days post-randomisation (via text/online questionnaire)

- Standardised symptom checklist including those commonly associated with UTIs, and those associated with side effects of cefalexin.
- Any acute illnesses requiring assessment by a healthcare provider since last appointment with the CURLY research team, including whether any antibiotics were issued.
- Any additional/new antibiotic treatment since last appointment with the CURLY research team.
- Quality of life assessment (using CHU9D questionnaire).
- Health Resource Usage questionnaire.

9.1.7 Remote follow-up for recurrence at 30 days post-randomisation (urine sample collection at home)

- Urine sample collected at home and posted to lab.
- On receipt of urine sample at the local NHS lab, testing for urine microscopy, culture and antibiotic sensitivity.

9.2 Urine microbiological tests

9.2.1 Time points for urine sample collection

Urine samples will be collected at the following time points:

- Baseline ED visit as part of standard clinical assessment, following consent.
- Primary outcome assessment visit, 16 days post-randomisation.
- Follow-up for recurrence, 30 days post-randomisation.
- At any face-to-face review that takes place as a result of any acute event, if deemed to be clinically indicated.
9.2.2 Minimisation of urine contamination

As with standard clinical practice, it is essential to reduce contamination of urine samples during collection as this complicates the interpretation of culture results. Contamination occurs when urine flushes the vulva or glans and foreskin on voiding and becomes polluted with bacteria from normal skin bacteria (flora). This typically results in a mixed growth of multiple bacterial species.

Cleaning before collection can reduce the burden of incidental skin flora. To ensure that this cleaning is optimised, participating sites will be provided with standardised cleaning instructions which will be used for the clinical care of all participants throughout the duration of the trial. In addition, bag collection of urine will be avoided, as this is known to result in very high contamination rates and is not reliable for culture (41).

9.2.3 Urine sample collection in the ED

Collection within the ED will follow standard clinical practice:

(a) Infants and pre-continent children:

- Clean catch collection
- In-out-catheterisation (this is an alternative collection method which is commonly used in EDs for infants <1 year of age)

(b) Continent children:

Midstream urine collection

For clean catch and midstream urine collections, parents/guardians will receive standardised instructions for cleaning and collection, along with support from the ED nursing staff, as is standard practice.

Each urine specimen will be collected in a sterile universal container and, following early urine testing (see Section 9.2.5) will be processed at each site laboratory following the standard pathway at each site. Where the delay between specimen collection and laboratory processing exceeds 4 hours, refrigeration of the urine sample is essential. Samples may be refrigerated for up to 48 hours before processing, in line with UK Standards for Microbiological Investigations (42).

